3. TARGETED STUDY POPULATION

3.1. General Characteristics

The study populations will be healthy spherical habitual contact lens wearers between 18-69 years of age.

3.2. Inclusion Criteria

Potential subjects must satisfy all of the following criteria to be enrolled in the study:

1. Subjects must be 18-69 years of age (inclusive)
2. Subjects must be habitual disposable hydrogel or silicone hydrogel (1-day, 2-week, or monthly replacement schedule) soft lens wearer in both eyes. Habitual is defined as at least one (1) month of contact lens wear where the lenses are worn for a minimum of six (6) hours per day and a minimum of five (5) days per week
3. Subjects must have best corrected visual acuity of 20/25 (Snellen or equivalent) or better in each eye
4. The subject's spherical refraction (vertexed) must be between -1.00 and -6.00 D in each eye
5. The subject's refractive cylinder must be less than or equal to -1.00 D in each eye
6. The subject must have normal eyes (i.e., no ocular medications or infections of any type)
7. Subjects must possess a functional/usable pair of spectacles and bring them to the visit (only if applicable - to the investigators discretion)
8. Subjects must read, understand, and sign the Statement of Informed Consent
9. Subjects must appear able and willing to adhere to the instructions set forth in this clinical protocol.

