Eligibility Criteria	
Potential subjects must satisfy all of the following criteria to be enrolled in the study:
 
 1. Subjects must be 18-69 years of age (inclusive) 2. Subjects must be habitual disposable hydrogel or silicone hydrogel (1-day, 2-week, or monthly replacement schedule) soft lens wearer in both eyes. Habitual is defined as at least one (1) month of contact lens wear where the lenses are worn for a minimum of six (6) hours per day and a minimum of five (5) days per week 3. Subjects must have best corrected visual acuity of 20/25 (Snellen or equivalent) or better in each eye 4. The subject's refractive sphere (vertexed) must be between -1.00 and -6.00 D in each eye. 5. The subject's refractive cylinder must be less than or equal to -1.00 D in each eye 6. The subject must have normal eyes (i.e., no ocular medications or infections of any type) 7. Subjects must possess a functional/usable pair of spectacles and bring them to the visit (only if applicable - to the investigators discretion) 8. Subjects must read, understand, and sign the Statement of Informed Consent 9. Subjects must appear able and willing to adhere to the instructions set forth in this clinical protocol. 
Potential subjects who meet any of the following criteria will be excluded from participating in the study:
 
 1. Currently pregnant or breast-feeding 2. Diabetes 3. Any ocular or systemic allergies or disease which may interfere with contact lens wear (at the discretion of the investigator) 4. Any systemic disease, autoimmune disease, or use of medication which may interfere with contact lens wear (at the discretion of the investigator) 5. Any infectious diseases (e.g. hepatitis, tuberculosis) or a contagious immunosuppressive disease (eg, HIV), by self-report 6. Current habitual use of Restasis, Xiidra, ocular steroids, or any medication (RX or OTC) that may interfere with contact lens wear (at the discretion of the investigator) 7. Grade 2 or greater corneal staining or conjunctival injection on the FDA scale

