6. STUDY INTERVENTION

6.1. Identity of Test Articles

The following contact lens will be used in this study:

Table 2: Test Article

	Washout Lens	Randomization lens Arm 1	Randomization lens Arm 2	Randomization lens Arm 3
Name	1-DAY ACUVUE® MOIST	ACUVUE® 2	ACUVUE® OASYS®	ACUVUE® Vita®
Manufacturer	Johnson and Johnson Vision Care, Inc.			
Compass Protocol(s)	17CP1339	17CP1339	17CP1339	17CP1339
Lens Material	Etafilcon A	Etafilcon A	Senofilcon A	Senofilcon C
Nominal Base Curve @ 22°C	8.5	8.3	8.4	8.4
Nominal Diameter @ 22°C	14.2	14.0	14.0	14.0
Nominal Distance Powers (D)	-1.00 to -6.00D	-1.00 to -6.00D	-1.00 to -6.00D	-1.00 to -6.00D
Modality in Current Study	Daily	Daily	Daily	Daily
Replacement Frequency in Current Study	Daily	Daily	Daily	Daily
Packaging Form (vial, blister, etc.)	Blister	Blister	Blister	Blister

All Subjects will wear Moist and will be randomized into one of the other lens types. Each subject will wear approximately fifty 1-DAY ACUVUE® MOIST® and eight of the other lens type.

The following lens care systems will be used in this study:

Table 3: Lens Care Systems

	Test	Control 1	Control 2
Solution Name/Description	Revitalens®	OPTI-FREE PureMoist	Clear Care
Manufacturer	Johnson & Johnson, Inc	Alcon, Inc	Alcon, Inc

Lenses will be soaked in the appropriate solution by an unmasked staff member at the site and transferred to the investigator in an unmarked lens case for lens insertion by the subject.

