1.11	Slit Lamp Biomicroscopy	
FDA Slit Lamp Classification Scale will be used to grade the findings and determine eligibility.
 
If there are any Grade 2 or higher corneal staining or conjunctival injection, or Grade 3 or higher other slit-lamp findings, the subject is ineligible to continue at this time, but may return up to one additional time to determine eligibility. If discontinued a final examination must be completed.
 
Note 1: The following [redacted] will be used to assess specific ocular physiology in greater detail:
 
 • [redacted] Limbal and conjunctival redness • [redacted] Expanded Corneal staining • [redacted] Conjunctival staining 
If the clearance of the fluorescein needs to be expedited, preservative-free rewetting drops or saline may be instilled.
	[redacted] [redacted] [redacted] [redacted]
1.12	Eligibility after Baseline	All responses to Inclusion Criteria questions must be answered "yes" and all responses to Exclusion Criteria questions must be answered "no" for the subject to be considered eligible.	

Visit 1: Washout Lens Fitting			
Step	Procedure	Details	
1.13	Lens Selection	All subjects will be fit in 1-DAY ACUVUE® MOIST as a washout lens. Subjects will be corrected for distance vision only.	
1.14	Lens Insertion	The subject inserts the study lenses. Check for lens damage under the slit lamp before proceeding with lens settling. Replace damaged lenses, if applicable.	
1.15	Lens Settling	Allow the study lenses to settle for a minimum of 5 minutes.	
1.16	Visual Acuity	Record the distance Snellen visual acuity with the contact lenses (OD, OS) to the nearest letter. Subjects must read the smallest line until at least 50% of the letters are read incorrectly.	
1.17	Subjective Best Sphere Over Refraction	Perform a distance spherical over-refraction OD and OS using any acceptable means (i.e., phoropter, trial lenses, flipper bars) in normal room illumination and record the resultant distance Snellen visual acuity OD and OS. A plano spherical over-refraction must be achieved.	
1.18	Lens Power Modification (if applicable)	Adjust the lens power if the subject's best sphere over-refraction is outside of plano. For each power modification, remove the lens, assign the new lens power, and repeat steps (1.15-1.19). Record the resultant distance Snellen visual acuity OD and OS. Up to two power modifications are allowed.	

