		
 • Subjects may use reading glasses over study contact lenses as needed • A patient instruction guide will be provided. • Subjects will be scheduled for Visit 2 in approximately 5-7 days. 
* Note: In the event a lens is lost or damaged, the subject will return to the clinical site for replacement. As much as reasonably possible, a damaged lens and packaging should be returned to the clinical site (wet, if possible) and then returned to the Sponsor. If lens damage is present, complete the Product Quality Complaint Form, if applicable. The lens will be stored in labeled vial with study provided solution, and clearly differentiated from the other worn lenses that will be shipped back to the Sponsor.

1.26	Randomization	Subjects will be randomized to a contact lens arm and a solution order. The same power lenses as fit in Visit 1 will be used in all remaining visits. (this will allow time for lenses to be soaked 16-28 hours)

Prior to Visit 2, randomized lenses will be prepared.

Sixteen to twenty-eight hours prior to Visit 2, the subject's lenses will be soaked in the test solutions in the sponsor provided lens cases. (See work aid for lens preparation instructions)

VISIT 2

The subjects must present to Visit 2 wearing their habitual spectacles (if applicable) having not worn any lenses or used any artificial tears that day.

Visit 2: Follow-up of Washout lenses		
Step	Procedure	Details
2.1.	Adverse Events and Concomitant Medications Review	Review any changes to the subject's medical history or concomitant medications from the previous study visit. Record any changes, and any adverse events.
2.2.	Compliance	Confirm compliance with the dispensed Washout lenses.

Visit 2: Follow-up of Washout lenses		
Step	Procedure	Details
2.3.	Subject Reported Ocular Symptoms	Subjects will respond to a verbal open-ended symptoms questionnaire. [REDACTED]
2.4.	Follow-Up modified CLDEQ-8 Questionnaires	The subject will respond to the Follow-Up modified CLDEQ-8 Questionnaires. Note: instruct the patient to think about how their wash-out contact lenses feel on an average day and answer the questions based on this level of comfort. Appendix A
2.5.	Visual Acuity	Record the distance Snellen visual acuity with their habitual spectacles (OD, OS, and OU) to the nearest letter. Subjects must read the smallest line until at least 50% of the letters are read incorrectly. [REDACTED]

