ACUVUE® VITA Brand Contact Lenses are indicated for daily wear for the optical correction of refractive ametropia (myopia and hyperopia) in phakic or aphakic persons with non-diseased eyes who may have 1.00D or less of astigmatism.

ACUVUE® VITA Brand Contact Lenses for ASTIGMATISM are indicated for daily wear for the optical correction of refractive ametropia (myopia and hyperopia) in phakic or aphakic persons with non-diseased eyes who may have 0.50D to 3.00D of astigmatism.

The lenses contain a UV Blocker to help protect against transmission of harmful UV radiation to the cornea and into the eye.

These lenses are intended for frequent/planned replacement wear (see **REPLACEMENT SCHEDULE** section). Lenses may be disinfected using a chemical disinfection system only and should be discarded after the recommended wearing period as prescribed by the Eye Care Professional. These lenses are intended for daily wear, monthly replacement.

CONTRAINdications (REASONS NOT TO USE)

DO NOT USE these lenses when any of the following conditions exist:

- Acute or subacute inflammation or infection of the anterior chamber of the eye.
- Any eye disease, injury, or abnormality that affects the cornea, conjunctiva, or eyelids.
- Severe insufficiency of lacrimal secretion (dry eye).
- Corneal hypoesthesia (reduced corneal sensitivity).
- Any systemic disease that may affect the eye or be exaggerated by wearing contact lenses.
- Allergic reactions of ocular surfaces or adnexa that may be induced or exaggerated by wearing contact lenses or use of contact lens solutions.
- Ocular irritation due to allergic reactions which may be caused by use of contact lens solutions (e.g., cleaning and disinfecting solutions, rewetting drops, etc.) that contain chemicals or preservatives (such as mercury, Thimerosal, etc.) to which some people may develop an allergic response.
- Any active corneal infection (bacterial, fungal, protozoal, or viral).
- If eyes become red or irritated.

WARNINGS

Patients should be advised of the following warnings pertaining to contact lens wear:

EYE PROBLEMS, INCLUDING CORNEAL ULCERS, CAN DEVELOP RAPIDLY AND LEAD TO LOSS OF VISION. IF THE PATIENT EXPERIENCES:

- Eye Discomfort,

- **Excessive Tearing,**
- **Vision Changes,**
- **Loss of Vision,**
- **Eye Redness, or**
- **Other Eye Problems,**

**THE PATIENT SHOULD BE INSTRUCTED TO
IMMEDIATELY REMOVE THE LENSES AND PROMPTLY
CONTACT THE EYE CARE PROFESSIONAL.**

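### Inclusion item 5 states the cylinder limit with the inequality reversed; secondarily, item 4 admits a few high-minus eyes that the supplied lens powers cannot bring to the required plano over-refraction

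*Combined protocol and SAP*

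**What the plan says.** **Cylinder.** Item 5 in section 3.2, and in the same words in the synopsis, requires: "refractive cylinder must be less than or equal to -1.00 D in each eye". No exclusion criterion in section 3.3 caps astigmatism. Section 3.1 describes the population as wearers of spherical lenses. In Appendix C the VITA sphere insert covers people with "non-diseased eyes who may have 1.00D or less of astigmatism", and the OASYS sphere insert gives the same 1.00 D limit as a magnitude.

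**Sphere and lens power.** Item 4 in section 3.2 says "spherical refraction (vertexed) must be between -1.00 and -6.00 D in each eye"; the synopsis says "refractive sphere (vertexed) must be between -1.00 and -6.00 D in each eye". Table 2 in section 6.1 lists the washout lens and all three study lenses in -1.00 to -6.00 D only. At Visit 1 (section 7.2):

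- Step 1.17: "A plano spherical over-refraction must be achieved".
- Step 1.18: the lens power is changed, at most twice, if the "best sphere over-refraction is outside of plano".
- Step 1.24: continuation depends on acuity of 20/30 or better in each eye, acceptable fit and investigator approval. Plano is not listed.
- Step 1.26: "The same power lenses as fit in Visit 1 will be used in all remaining visits".

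**How eligibility is applied.** Steps 1.5 and 1.12 require a yes to every inclusion question.

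**The concern.** An inclusion criterion should select the intended population when it is applied as written. Item 5 does so only if the site sets its sign aside. Applied literally, it turns away the spherical wearers the study is meant for and admits astigmatic eyes beyond the OASYS and VITA labelling.

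The wording has operational force. Every criterion must be answered yes, edit checks are built into the EDC system (section 15.1), being eligible is part of the definition of a completer (section 8.1), and the sponsor may withhold payment for continuing an ineligible subject (section 20).

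Item 4 raises a separate, smaller problem. It bounds one component of the refraction, while the fitting step depends on the best sphere. An eye can pass every criterion and still be unable to satisfy a mandatory step with the lenses on hand, and the protocol does not say what the site should then do.

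**Working it through.** No stated figure in the plan bears on this point, and the sample size was not based on a power calculation (section 14.2). The check is a reading of the inequality followed by an enumeration.

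**1. Item 5 as a signed inequality (cylinder ≤ -1.00 D).**

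| Cylinder (D) | 0.00 | -0.25 | -0.50 | -0.75 | -1.00 | -1.25 | -1.75 | -2.50 | -3.00 |
|---|---|---|---|---|---|---|---|---|---|
| Passes? | no | no | no | no | yes | yes | yes | yes | yes |

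Four of the five quarter-dioptre values from 0.00 to -1.00 D fail, and no value is too large to pass. The inserts' limit of 1.00 D or less would admit all five and reject everything beyond -1.00 D.

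**2. Item 4 against Table 2, with item 5 read as a magnitude of at most 1.00 D.**

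Inputs: sphere -1.00 to -6.00 D in 0.25 D steps (21 values, item 4); cylinder 0.00 to -1.00 D in 0.25 D steps (5 values); strongest supplied lens -6.00 D (Table 2). This gives 21 × 5 = 105 combinations.

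Assumption: best sphere = sphere + cylinder/2. The documents do not define best sphere.

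| Sphere / cylinder (D) | Best sphere (D) | Shortfall beyond -6.00 D |
|---|---|---|
| -5.75 / -0.75 | -6.125 | 0.125 |
| -5.75 / -1.00 | -6.25 | 0.25 |
| -6.00 / -0.25 | -6.125 | 0.125 |
| -6.00 / -0.50 | -6.25 | 0.25 |
| -6.00 / -0.75 | -6.375 | 0.375 |
| -6.00 / -1.00 | -6.50 | 0.50 |

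Six of 105 combinations lie beyond the supplied range, four of them by at least 0.25 D. Spheres up to -5.50 D are all correctable (-5.50 - 1.00/2 = -6.00). The weak end is safe: the weakest best sphere is -1.00 D.

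**3. Sensitivity to vertexing the cylinder.** Item 4 vertexes the sphere; the documents do not say whether the cylinder is vertexed, and give no vertex distance d. Take s as the vertexed sphere and c as the spectacle-plane cylinder. The spectacle-plane sphere is F = s/(1 + d·s), the second meridian is G = F + c, and its vertexed value is G/(1 - d·G). The best sphere is the mean of s and that value.

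For -6.00/-1.00 at an assumed d of 0.012 m: F = -6.466, G = -7.466, vertexed -6.852, best sphere -6.426, shortfall 0.426 D. Over an assumed 10 to 14 mm the worst shortfall is 0.44 to 0.41 D. The same six combinations still exceed -6.00 D, but only two do so by 0.25 D or more.

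**4. Both items taken literally.** The gap widens with cylinder. At -2.00 D every sphere from -5.25 D is out of reach (-5.25 - 1.00 = -6.25). At -3.00 D every sphere from -4.75 D is (-4.75 - 1.50 = -6.25).

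**The case against.** The best reply on item 5 is that this is a slip of notation. Read with section 3.1 and the inserts, the intended magnitude is plain, and trained sites would probably apply it that way. Step 1.24 is also a second filter: an eye with large uncorrected cylinder must reach 20/30 in a spherical lens and have the investigator's approval before randomization at step 1.26. This stands as a limit on the consequences. It does not rescue the text, which is the rule against which eligibility and deviations are judged.

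On item 4, the sphere-plus-half-cylinder convention is an assumption, and the wording in section 3.2 is less definite than the synopsis. If it meant spherical equivalent, the mismatch would vanish; the synopsis wording points to the sphere component. Since step 1.24 omits plano, an under-corrected eye may simply continue. If it is instead lost, that happens before randomization, within the 120 - 108 = 12 places between enrolment and randomization (section 4.3).

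A reader might infer more than the documents support:

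- *That the study will in fact fill with high astigmats.* This needs sites or a programmed check to apply the signed value. How the eCRF handles item 5 is not documented.
- *That 4/105 = 3.8%, or 6/105 = 5.7%, of subjects are affected.* These are shares of grid cells, not of people. No refractive distribution is given.
- *That every lens insert sets 1.00 D.* The limit is clearly legible only for the OASYS and VITA spheres. The text for the ACUVUE 2 family is broken and shows both 0.75 D and 1.00 D, and the readable MOIST pages show no indication for the spherical lens.
- *That the primary result is biased.* Comfort is compared between eyes of the same subject, solutions are randomly assigned to eyes (section 5.1), and the Visit 1 power is kept throughout.

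**Conclusion.** The point on item 5 holds on the text alone: the inequality is reversed in both places and conflicts with section 3.1 and the two legible inserts. The point on item 4 also holds, as a secondary one. It is confined to spheres of -5.75 and -6.00 D with cylinder: 6 of 105 combinations, with a worst shortfall of 0.50 D, or 0.41 to 0.44 D if the cylinder is vertexed. It rests on the half-cylinder convention and on item 4 meaning the sphere component.

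How many subjects are affected cannot be derived from the documents. In my judgement the effect on the comfort comparison in this exploratory pilot is small. What is at stake is correct eligibility, consistency with labelling, and avoidable deviations. That is enough to correct the wording before enrolment, given how little the correction costs.

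**What to change.** 1. In section 3.2 and the synopsis, state item 5 as a magnitude: cylinder 0.00 to -1.00 D (1.00 D or less) in each eye. Make any eCRF eligibility check use the same rule. The cost is one line in two places.

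2. Reconcile item 4, Table 2 and steps 1.17, 1.18 and 1.24. One way is to define item 4 on the vertexed best sphere, -1.00 to -6.00 D, and to state how best sphere is calculated. This moves the boundary at both ends. On the quarter-dioptre grid the six combinations listed above become ineligible. Four weaker ones become eligible: -0.75 D sphere with -0.50, -0.75 or -1.00 D cylinder, and -0.50 D sphere with -1.00 D cylinder (for example, -0.75 - 0.50/2 = -1.00).

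3. If item 4 is to stay on the sphere component, the alternatives are to extend the powers in Table 2 or to state in steps 1.17 and 1.24 how an eligible eye that cannot reach plano is handled. The OASYS and VITA inserts list powers beyond -6.00 D, but extension would have to cover the washout lens and the ACUVUE 2 arm as well.

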3.3. Exclusion Criteria

Potential subjects who meet any of the following criteria will be excluded from participating in the study:

1. Currently pregnant or breast-feeding
2. Diabetes
3. Any ocular or systemic allergies or disease which may interfere with contact lens wear (at the discretion of the investigator)
4. Any systemic disease, autoimmune disease, or use of medication which may interfere with contact lens wear (at the discretion of the investigator)
5. Any infectious diseases (e.g. hepatitis, tuberculosis) or a contagious immunosuppressive disease (eg, HIV), by self-report
6. Current habitual use of Restasis, Xiidra, ocular steroids, or any medication (prescription or over-the-counter) that may interfere with contact lens wear (at the discretion of the investigator)
7. Grade 2 or greater corneal staining or conjunctival injection on the FDA scale
8. Clinically significant (Grade 3 or greater on the FDA scale) corneal edema, corneal vascularization, or any other abnormalities of the cornea (excluding corneal staining) which would contraindicate contact lens wear
9. Clinically significant (Grade 3 or greater on the FDA scale) tarsal abnormalities which might interfere with contact lens wear
10. Any active ocular abnormalities/conditions that may interfere with contact lens wear (at the discretion of the investigator)
11. Any corneal distortion due to previous rigid gas permeable lens wear, surgery or pathology
12. History of any ocular or corneal surgery (eg, RK, PRK, LASIK)
13. Habitual contact lens wear modality as extended wear
14. Participation in any pharmaceutical or medical device related clinical trial within 7 days prior to study enrollment
15. History of binocular vision abnormality or strabismus
16. Habitual wearers of rigid gas permeable lens within the past 3 months
17. Employees of investigational clinic (investigator, coordinator, and technician etc.) or family member of an employee of the clinic by self-report.

3.4. Enrollment Strategy

Study subjects will be recruited from the Institution/clinical site's subject database and/or utilizing Institutional Review Board (IRB) approved materials.

4. STUDY DESIGN AND RATIONALE

4.1. Description of Study Design

This is a multi-site, randomized, double-masked, contralateral (i.e. exposure to different lens care solutions in either eye), 2-treatment x 2-period crossover, dispensing (washout lenses only), five-visit study. Here we define treatment as a pair of a control solution (CLEAR CARE or OPTI-FREE) and a test solution (RevitaLens).

Each subject will be randomly assigned to wear either ACUVUE 2, ACUVUE OASYS or ACUVUE Vita throughout the study. Subjects will then be randomly assigned to wear in a random sequence two pairs of lenses soaked in control solutions and test solution. Over the course of the study, subjects will be exposed to control solutions in one eye and to test solution in the contralateral eye for 2 hours using pre-soaked contact lenses. A washout period will be incorporated between each exposure where subjects will be wearing 1-Day ACUVUE Moist, a daily disposable lens, for 5 to 7 days.

The study begins with an Initial Visit (Visit 1) where subjects will be consented and screened for eligibility criteria. Subjects who found to be eligible will be fit and dispensed with 1-DAYACUVUE® MOIST® for 5 to 7 days as a washout period (subjects will wear these lenses during all washout periods). Subjects will then return for Visit 2 where they will be fit with their first pair of soaked lenses based on the randomization scheme. After 45 min of lens wear, subjects will be scheduled for a follow-up visit (Visit 3) 5-7 days later. Visit 3 will follow the same procedures as Visit 2, but with a 2-hour wear period. A washout period of 5-7 between Visit 3 and Visit 4 will occur. Following the washout period, subjects will be fit with the second pair of pre-soaked lenses at Visit 4. After 45 min of lens wear, subjects will be scheduled for a follow-up visit (Visit 5) 5-7 days later (see below for more details).

Visit 1:

Visit 1 (Baseline/Fitting/Washout): Baseline CLDEQ-8, eligibility, fitting of 1-DAY ACUVUE® MOIST (washout lenses) (Insertion, ocular symptoms, visual acuity, lens fit, dispensing), randomization.

Washout (Subject wears 1-DAY ACUVUE® MOIST) 5-7 days

Period 1: Solution 1 and Solution 2 soaked lenses

Visit 2 (Baseline/Fitting/45 min Follow-up): Modified CLDEQ-8, slit-lamp eligibility, fitting of lens pair #1 (Insertion, ocular symptoms, VAS comfort rating, visual acuity, lens fit, surface characteristics). 45 minutes of lens wear. Follow-up on lens pair #1 (ocular symptoms, VAS comfort rating, visual acuity, lens fit, surface characteristics, slit-lamp).

Washout (subject wears 1-DAY ACUVUE® MOIST) 5-7 days

Visit 3 (Fitting/120 min Follow-up/Washout): Modified CLDEQ-8, slit-lamp eligibility, fitting of lens pair #2 (Insertion, ocular symptoms, VAS comfort rating, visual acuity, lens fit, surface characteristics). 120 minutes of lens wear. Follow-up on lens pair #2 (ocular symptoms, VAS comfort rating, visual acuity, lens fit, surface characteristics, slit-lamp).

Washout (subject wears 1-DAY ACUVUE® MOIST) 5-7 days

Period 2: Solution 1 and Solution 3 soaked lenses

Visit 4 (Baseline/Fitting/45 min follow-up): Modified CLDEQ-8, slit-lamp eligibility/fitting of lens pair #3 (Insertion, ocular symptoms, VAS comfort rating, visual acuity, lens fit, surface characteristics). 45 minutes of lens wear/Follow-up on lens pair #3 (ocular symptoms, VAS comfort rating, visual acuity, lens fit, surface characteristics, slit-lamp).

Visit 5 (Fitting/120 min Follow-up): Modified CLDEQ-8, slit-lamp eligibility, fitting of lens pair #4 (Insertion, ocular symptoms, VAS comfort rating, visual acuity, lens fit, surface characteristics). 120 minutes of lens wear. Follow-up on lens pair #4 (ocular symptoms, VAS comfort rating, visual acuity, lens fit, surface characteristics, slit-lamp). Final evaluation.

